### **Period**

The period 2 starts from the first dose on Day 1 visit; the period 2 end date is the end of treatment date in period 2. The period 3 starts from first dose in period 3; the period 3 end date is defined as the end of treatment date in period 3. The period 4 starts on the day after the end of treatment in period 2/3. Assignment of events to each period will be based on date and time. When time is missing or not reported, the assignment will be based on date only; in that case, events starting on the date of first dose in period 3 will be assigned to the period 3 for those who are entering period 3, or to the safety follow-up period.

### **Visit windowing**

For the efficacy analysis, when visit windows are used, all visits will be re-aligned, i.e., they will be mapped into one of the visit windows. E.g., if the *Week 4* visit of a subject is delayed and occurs on Day 46 instead of on Day 28, it will be re-aligned to visit window *Week 8*. In the case of major deviations from the visit schedule, or due to unscheduled visits, several assessments of a subject may fall in a particular visit window (either scheduled or unscheduled). The rule to derive the visit windows are given in the Appendix 5.1.

## **2.2 Analysis sets**

**Enrolled set (ENR):** All subjects who signed the informed consent are included in the Enrolled Set. The enrolled set will be used when screening information needs to be presented.

**Randomized set (RAN):** All patients randomized are included in the Randomized Set. Patients will be analyzed according to the treatment assigned to at randomization. Unless otherwise

specified, mis-randomized patients (randomized in IRT by mistake) will be excluded from the randomized set. The RAN will be used for summaries of patient disposition and analysis sets.

**Full analysis set (FAS):** comprises all patients in the RAN to whom study treatment has been assigned. Following the intent-to-treat principle, patients will be analyzed according to the treatment assigned to at randomization, but actual stratum. FAS will be used for all efficacy variables, unless otherwise stated.

**Per Protocol set (PPS):** includes all FAS patients who are not excluded due to major protocol deviations (see [Section 5.6](#)).

**Safety set (SS):** includes all patients who received at least one dose of study medication. Patient will be analyzed according to treatment received and the actual stratum at baseline. The safety set will be used in the analysis of all safety variables.

### **2.2.1 Subgroups of interest**

Subgroups of interest are listed below. These will not necessarily be applied to all analyses but used as specified in the protocol or this SAP.

- stratification factor baseline ESSDAI score <10 or  $\geq 10$
- geographic region

### **2.3 Patient disposition, demographics and other baseline characteristics**

The analyses described in this section will be based on RAN and presented by the treatment groups initially randomized.

Summary statistics will be presented for continuous demographic and baseline characteristic variables for each treatment group and for all patients in the randomized set. The number and percentage of patients in each category will be presented for categorical variables for each treatment group and all patients.

The following demographic variables and baseline disease characteristics will be summarized by treatment group:

- Demographics:
  - Continuous variables: age, weight, height, BMI, time since diagnosis

- Categorical variables: Gender, race, ethnicity
- Baseline Disease Characteristics:
  - Continuous variables: ESSDAI , ESSPRI (pain, fatigue, dryness), PhGA (physician-assessed global VAS score), PaGA (patient assessed VAS score for global disease) , stimulated and unstimulated salivary flow, [REDACTED], Immunoglobulin level (IgG and IgM), SF-36 score (PCS and MCS), FACIT-F score, [REDACTED]
  - Categorical variables: ESSDAI stratum (<10 or  $\geq$ 10), use of DMARDs (split by type – to be defined further in PDS), [REDACTED] history of prior biologics treatment use (Yes/No), [REDACTED] Hypergammaglobulinemia (Yes if above ULN of IgG or IgM), Systemic signs (Glandular, Pulmonary, Neurologic or Articular, where 0=no sign), Steroid therapy (Yes/No) (A steroid conversion table is provided in Section 5.6 to calculate the amount of steroid use if needed)

## Medical history

Any significant prior or active medical condition at the time of signing informed consent will be coded using the MedDRA dictionary. These medical conditions will be summarized by primary system organ class and preferred term.

### 2.3.1 Patient disposition

The RAN will be used for summaries of patient disposition and analysis sets.

The patient disposition will be summarized by treatment group for different study periods (Period 2, Period 3 and Period 4). The following treatment group will be used for each period:

- Period 2: Placebo, VAY736 5 mg, VAY736 50 mg, VAY736 300 mg, Any VAY736, All
- Period 3: VAY736 150 mg, VAY736 300 mg -> Placebo, VAY736 300 mg -> VAY736 300 mg, Any VAY736
- Period 4: Placebo, VAY736 5 mg, VAY736 50 mg, VAY736 150 mg, VAY736 300 mg, VAY736 300 mg -> Placebo, VAY736 300 mg -> VAY736 300 mg, All

The number and percent of patients screened, randomized, completed and discontinued from the study will be summarized with reasons for discontinuation.

The number of patients with major protocol deviations and protocol deviations leading to exclusion from per-protocol set will be tabulated by category and deviation for the Randomized set.

The number of patients included in each analysis set will be tabulated. Patient exclusion from analysis populations will be listed for all patients with reasons for exclusion.

## **2.4 Treatments (study treatment, rescue medication, concomitant therapies, compliance)**

### **2.4.1 Study treatment / compliance**

The analysis of study treatment data will be based on the safety set.

The analysis will be summarized by the following treatment:

- Placebo
- VAY736 5 mg
- VAY736 50 mg
- VAY736 150 mg
- VAY736 300 mg
- Any VAY736

Duration of exposure of a treatment will be defined as following:

Duration of exposure (days) = end of treatment date – date of first dose + 1

Duration of exposure (weeks) = duration of exposure (days)/7

Note: Specifically in the calculation of duration of exposure, for VAY736 300 mg ->Placebo patients, end of treatment date is the end of treatment date (EoT) in period 2;

For Placebo->VAY736 150 mg patients, end of treatment date for placebo is the the end of treatment date (EoT) in period 2. The date of first dose for VAY736 150mg is the date of first administration of VAY736 150mg .

The cumulative duration of exposure to study treatment (the number and percentage of patients) will be summarized by treatment group (any, ≤ 4 Weeks, 5 - 8 Weeks, etc. up to 49 - 52 weeks).

### **2.4.2 Prior and concomitant medication**

Prior medications are defined as treatments taken and stopped prior to first dose of study treatment. Any medication given at least once between the day of first dose of randomized study treatment and the date of the last study visit will be a concomitant medication, including those which were started pre-baseline and continued into the period where study treatment is administered.

Prior and concomitant medications will be summarized in separate tables for SAF. Medications will be presented in alphabetical order, by Anatomical Therapeutic Classification (ATC) codes and grouped by anatomical main group. Tables will show the overall number and percentage of patients receiving at least one treatment of a particular ATC code and at least one treatment in a particular anatomical main group.

The number and percentage of patients receiving systemic therapies for pSS as prior and concomitant background medication will be presented separately by preferred term.

## 2.5 Analysis of the primary objective

### 2.5.1 Primary endpoint

The following estimand framework is adopted for the primary analysis.

- Population: FAS
- Variable of interest: Change from baseline in ESSDAI total score after 24 weeks of VAY736 or placebo administration every four weeks. This will be defined as the Week 24 ESSDAI value minus the baseline ESSDAI value with negative values indicating improvement in disease status.
- Intercurrent events: Regardless whether early termination from the study, interruption of study treatment, or intensified concomitant treatment (local and systemic) has occurred.
- Summary measure: Adjusted mean change from baseline in ESSDAI total score at Week 24 will be calculated from MMRM.

### Statistical hypothesis, model, and method of analysis

The primary analysis will be based on FAS.

The primary objective of this study is to demonstrate a dose response of VAY736 defined as change in ESSDAI from baseline at 24 weeks.

[REDACTED]

[REDACTED]

[REDACTED]

[REDACTED]

[REDACTED]

[REDACTED]

### **2.5.2 Handling of missing values/censoring/discontinuations**

The planned primary repeated measures mixed effects model assumes that missing values are missing at random. The reasonableness of this assumption will be checked during the blinded review of the data and if necessary further methods may be applied.

Sensitivity analyses of imputing might be considered to test the robustness of the results to the missing data assumptions. The following approaches could be explored:

- impute data based on the placebo treatment group data;
- impute data based on patients' data who discontinued treatment but continued study visits in case a sufficiently high number of such cases is observed.

### **2.5.3 Supportive analyses**

#### **Per Protocol Analysis**

To assess the potential influence of adherence to study procedures on the results of the primary analysis, the full dose response modeling analysis as described in [Section 2.5.2](#) will be repeated based on per protocol set.

#### **Responder Analysis**

Responder status in ESSDAI will be assessed at week 12 [REDACTED]

[REDACTED]

## 2.6 Analysis of the secondary objective

### 2.6.1 Secondary endpoint

The following secondary variables will follow same estimand definition as primary efficacy endpoint.

The secondary variables include change from baseline in ESSPRI, FACIT-F, SF-36 (PCS and MCS), PhGA, PaGA and salivary flow rate (unstimulated and stimulated) over 24 weeks.

### 2.6.2 Statistical hypothesis, model, and method of analysis

The same dose-response analysis using MCPMod for primary endpoint will be done on the ESSPRI and FACIT-F score.

[REDACTED]

[REDACTED]

[REDACTED]

[REDACTED]

[figure not shown]
[REDACTED]

[REDACTED]

### 2.6.3 Handling of missing values/censoring/discontinuations

For the secondary analyses, missing data will not be imputed. If missing data occurs in a domain the corresponding total measurement will be set to missing. If a baseline assessment is missing (and there is no the screening value available to replace it) the corresponding change from baseline value will be missing.

[REDACTED]

## 2.7 Safety analyses

All safety variables will be analyzed on based on the safety set.

### 2.7.1 Adverse events (AEs)

The number (and proportion) of patients with treatment emergent adverse events (events started after the first dose of investigational drug or events present prior to start of double-blind treatment but increased in severity based on preferred term) will be summarized in the following ways:

- by treatment, primary system organ class (SOC) and preferred term (PT).
- by treatment, primary system organ class, preferred term and maximum severity.
- by treatment, Standardized MedDRA Query (SMQ) and preferred term.

Separate summaries will be provided for study medication related adverse events, death, serious adverse events, other significant adverse events leading to discontinuation.

As appropriate, the exposure-adjusted event rate (EAER) defined as below will be presented:

$$EAER = \frac{\sum \# \text{ of events}}{\sum \min(\text{study cutoff}, \text{end of study})}$$

A graphical display of relative frequencies within system organ classes and relative risks, as appropriate, will be presented.

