3.1 Study design

This is a randomized, double-blind, placebo-controlled, multicenter, parallel-group trial in approximately 180 patients with active pSS. The study is divided into 4 study periods:

Period 1: A screening period of 4 weeks to assess patient eligibility. Patients can be re-screened only once and no study-related re-screening procedure should be performed prior to written re-consent by the patient.

Period 2: At baseline, eligible patients will be randomized to one of three VAY736 dose arms (VAY736 5 mg, 50 mg or 300 mg s.c.) or a placebo arm. Blinded study drug will be administered every four weeks for a 24-week period. Approximately 45 patients will be randomized per treatment group. [REDACTED], randomization will be stratified by:

- baseline ESSDAI score (<10 or ≥ 10 based on weighted scores)

[REDACTED]

The primary endpoint will be assessed at the end of period 2 (week 24).

[figure not shown]
Treatment assignment in period 2 will remain double blinded until the end of period 3.

Period 3: After week 24 assessments, patients in the VAY736 300 mg arm will be re-randomized in a 1:1 ratio to either continue VAY736 300 mg s.c. every four weeks or switch to [REDACTED] placebo up to week 52. Patients who received placebo during period 2 will be switched to VAY736 150 mg s.c every four weeks up to week 52. Patients who received 5 mg and 50 mg s.c. in period 2 will proceed directly to period 4. Treatment assignment in period 3 will remain double blinded until the end of the study period.

Period 4: The safety follow-up period lasts for a minimum of 20 weeks from last dose administration of VAY736, or longer (with reduced visit frequency) [REDACTED]

[REDACTED] Patients who will be treated with another immunmodulatory or immunsuppressive treatment (e.g. azathioprine, cyclophosphamide, high dose glucocorticosteroids) after completion of the minimum 20 week safety follow-up period are excluded from further safety follow-up.

The primary efficacy analysis will be performed when all patients have completed the week 24 study visit. An interim analysis will occur when approximately 100 patients have completed their Week 24 visit.

Figure 3-1 Study design

*Only patients in the period 2 VAY736 300 mg arm will be eligible for period 3 re-randomization.

[figure not shown]

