- 50 mg dose arm (period 2): The unblinded pharmacist will make the necessary dilution of the solution for s.c. injection as detailed in the pharmacist's manual. The patient will receive one injection of the diluted solution for s.c. injection and one injection of generic placebo.
- 150 mg dose arm (period 3): No dilutions are necessary for this dose level. The patient will receive 1 mL of solution for injection (as after reconstitution) and another injection of generic placebo.
- 300 mg dose arm (period 2 and period 3): IRT will dispense two vials of VAY736 powder for solution. The powder will be reconstituted and the patient will receive two injections of 1 mL each, 150 mg/mL VAY736 solution for s.c. injection.

Generic placebo:

Liquid placebo [REDACTED], for s.c. injections.

Please refer to the pharmacist's manual for further instructions on reconstitution and dilution of VAY736.

Please see [Table 6-1](#) and [6-2](#) for scheduling of IRT contact and administration of study medication and pre-medication. Doses will be administered once every four weeks for 24 weeks in period 2 and once every four weeks for 28 weeks in period 3. The last doses administered in period 2 and 3 will occur on study scheduled visit 106 and 207, respectively.

For the first administration for all patients in period 2 and 3, the patient must remain at the study center for observation for at least 6 hours or longer as per local requirements.

[REDACTED]

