9.5.2 Safety variables

All safety variables will be analyzed on based on the safety set.

The number (and percentage) of patients with treatment emergent adverse events (events started after the first dose of investigational drug or events present prior to start of double-blind treatment but increased in severity based on preferred term) will be summarized in the following ways:

- by treatment, primary system organ class (SOC) and preferred term (PT).
- by treatment, primary system organ class, preferred term and maximum severity.
- by treatment, Standardized MedDRA Query (SMQ) and preferred term.

Separate summaries will be provided for study medication related adverse events, death, serious adverse events, other significant adverse events leading to discontinuation.

As appropriate, the incidence of AEs will be presented per 100 patient years of exposure.

A graphical display of relative frequencies within system organ classes and relative risks, as appropriate, will be presented.

Injection reactions

Injection reactions will be summarized by type of injection reaction (overall, local and systemic), by grading, and by visit.

Laboratory data

The summary of laboratory evaluations will be presented for [REDACTED] of laboratory tests [REDACTED].

Descriptive summary statistics for the change from baseline to each study visit will be presented by test group, and laboratory test .

Shift tables based on the normal laboratory ranges will also be provided. For the shift tables, the normal laboratory ranges will be used to evaluate whether a particular laboratory test value was normal, low, or high for each visit value relative to whether or not the baseline value was normal, low, or high. These summaries will be presented by laboratory test category.

The number and percentage of patients with clinically notable laboratory results after baseline will be presented.

Immunogenicity

All the results for immunogenicity data (anti-VAY736 antibodies) will be listed by visit/time.

If appropriate, summary statistics and shift tables will also be presented.

Vital signs

Analysis of the vital sign measurements using summary statistics for the change from baseline for each post-baseline visit will be performed. These descriptive summaries will be presented by vital sign.

ECG

Summary statistics will be presented for ECG variables by visit. Qualitative changes will be summarized.

[figure not shown]
[figure not shown]

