## 2.1.1 General definitions

### Study treatment

The following grouping scheme / data selection will be used for reporting of safety summary:

Grouping Scheme 1 (short term summary, up to 24 weeks): only data on or before the end of treatment (defined below) in period 2 will be tabulated. The treatment used will be according to the treatment groups initially received:

Placebo  
VAY736 5 mg  
VAY736 50 mg  
VAY736 300 mg  
Any VAY736

Grouping Scheme 2 (long term summary, all study periods):

VAY736 5 mg  
VAY736 50 mg  
VAY736 150 mg  
VAY736 300 mg 24 Weeks (this group includes patients receiving VAY736 300 mg and stopping treatment in period 2, as well as those receiving placebo in period 3)  
VAY736 300 mg 52 Weeks  
Any VAY736 300 mg  
Any VAY736

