### Treatment-emergent adverse event

A treatment-emergent adverse event (AE) is defined as any adverse event started after the first dose of study treatment or events present prior to the first dose of study treatment but increased in severity based on preferred term (PT).

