## 4 Change to protocol specified analyses

Not applicable.

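### The SAP's exposure-adjusted AE rate divides by follow-up time, contrary to the protocol and the SAP's own exposure definition, with no change declared and no grouping scheme named

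*SAP*

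**What the plan says.** Protocol 9.5.2 plans that, as appropriate, "the incidence of AEs will be presented per 100 patient years of exposure". Protocol 9.3 defines treatment duration as last administration minus first administration plus 28 days.

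SAP 2.4.1 defines exposure as end of treatment date minus first dose date plus 1. It handles the switching arms explicitly. Placebo exposure, and exposure of 300 mg patients moved to placebo, stops at the period 2 end of treatment. For the 150 mg group, "The date of first dose for VAY736 150mg is the date of first administration of VAY736 150mg".

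SAP 2.7.1 then states that, as appropriate, "the exposure-adjusted event rate (EAER) defined as below will be presented". The formula divides the number of events by the sum over patients of min(study cutoff, end of study). It has no first-dose, last-dose or end-of-treatment term and no unit. The compound-specific paragraph of 2.7.1 also promises exposure-adjusted incidence rates for the safety-plan risks, without a visible denominator.

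SAP 2.1.1 sets two safety groupings. In Scheme 1, "only data on or before the end of treatment (defined below) in period 2 will be tabulated". Scheme 2 covers all study periods. A treatment-emergent AE "is defined as any adverse event started after the first dose of study treatment" (or one that worsened), with no end date. SAP section 4, "Change to protocol specified analyses", reads as not applicable.

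**The concern.** The label promises a rate per unit of exposure, while the formula delivers a rate per unit of time in study. These differ in this trial because every patient has off-drug follow-up of at least 20 weeks after the last VAY736 dose, and because paths split at week 24. The 5 and 50 mg patients go straight to follow-up, placebo patients move to 150 mg until week 52, and 300 mg patients are re-randomised to 300 mg or placebo until week 52.

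If the formula met the Scheme 1 event window, about 24 weeks of events would be divided by time running to end of study. For placebo patients that time includes treatment with active 150 mg. Scheme 1 is the placebo-controlled safety summary, so differences between arms in reported rates would partly reflect how long each arm was followed.

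**Working it through.** The documents give no rate to reproduce. The check sets the definitions side by side and then does person-time arithmetic for completers.

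**Definitions, for a patient completing period 2**
- Protocol 9.3: doses from week 0 to week 20, so 140 + 28 = 168 days.
- SAP 2.4.1: end of treatment at about day 168, so about 168 days.
- SAP 2.7.1 formula: time to end of study or study cutoff, whichever is smaller. This matches neither of the above unless the cutoff is itself a period 2 cut.

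**Inputs for end of study**
- Protocol 5.5.4: "The last doses administered in period 2 and 3 will occur on study scheduled visit 106 and 207". Tables 6-1 and 6-2 place these visits at weeks 20 and 48.
- Protocol 3.1: "The safety follow-up period lasts for a minimum of 20 weeks from last dose administration of VAY736". The minimum is therefore 20 + 20 = week 40 (5/50 mg) and 48 + 20 = week 68 (placebo then 150 mg).
- Protocol Tables 5-3 and 6-3: maximum week 128 (from period 2) and week 156 (from period 3).

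**Literal application to Scheme 1, equal true rates**

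Reported rate / true rate = 24 / weeks to end of study. The false rate ratio is the placebo denominator divided by the 5/50 mg denominator.

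| Follow-up | 5/50 mg | Placebo | 5/50 mg vs placebo |
|---|---|---|---|
| Both minimum | 24/40 = 0.60 | 24/68 = 0.35 | 68/40 = 1.70 |
| Both maximum | 24/128 = 0.19 | 24/156 = 0.15 | 156/128 = 1.22 |

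Variations:
- End-of-study visit 4 weeks after the minimum in both arms: 72/44 = 1.64.
- Assume 10% or 20% of placebo patients do not enter period 3 and leave at week 40: (0.9 × 68 + 0.1 × 40)/40 = 1.63; (0.8 × 68 + 0.2 × 40)/40 = 1.56.
- Opposite extremes, one whole arm at minimum and the other at maximum: 68/128 = 0.53 to 156/40 = 3.9.
- 300 mg versus placebo at minimum: 68/68 = 1.00 if all stay to week 68. If the half re-randomised to placebo leave at week 52 (assumption), the mean is (52 + 68)/2 = 60 weeks and the ratio is 68/60 = 1.13.
- Analysis at the week 24 milestone, assuming uniform accrual over 52 to 104 weeks: rates are 0.32 to 0.64 of the true value. The 5/50 mg versus placebo ratio is 1.24 to 1.51 with discharge near the minimum, and 1.00 if nobody is discharged before week 128.

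**In rate units.** Take 45 patients per arm and an assumed true rate of 200 events per 100 patient-years. Matched time is 45 × 168/365.25 = 20.7 patient-years, giving 41.4 events. At minimum follow-up the literal denominators are 45 × 280/365.25 = 34.5 and 45 × 476/365.25 = 58.6 patient-years. Reported rates would be 41.4/34.5 = 120 per 100 patient-years (5/50 mg) and 41.4/58.6 = 71 (placebo). With matched windows the ratio is 20.7/20.7 = 1.00.

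**Scheme 2.** Events and time both run through follow-up, so the windows can agree. The exception is the 150 mg group. If its clock started at the first placebo dose while only events from week 24 on were counted, 68 − 24 = 44 weeks of events would face 68 weeks of time at minimum follow-up, a factor of 44/68 = 0.65.

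**The case against.** The strongest reply is that the documents never pair this formula with Scheme 1. In Scheme 1 every completer contributes about 24 weeks, so a time-adjusted rate has least use there. The instruction to tabulate only data up to the period 2 end of treatment may naturally be read as limiting person-time as well as events. Study cutoff is undefined in the visible text and could be that cut. Parts of the SAP are blacked out, and a definition there cannot be ruled out. This stands: the Scheme 1 distortion is conditional.

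Two further replies also stand. Follow-up time is a legitimate denominator for treatment-emergent events without an end date, which covers Scheme 2. And the start of the clock is not wholly open, because SAP 2.1.1 counts study days from first dose; what remains open is mainly the 150 mg group.

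None of this touches the conflict of definitions. The visible formula carries an exposure label, departs from the protocol and from SAP 2.4.1, and is not declared in section 4. Nor does the optional status of the display settle the matter. The exposure-adjusted incidence rates for the safety-plan risks are promised without that qualifier, and this is the only visible exposure-adjusted formula from which their denominator could be taken.

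**Conclusion.** The conflict of label and denominator, and the missing declaration, are certain from the text. The point is minor to moderate: the rate is an as-appropriate display, and the n (%) AE tables and efficacy results do not depend on it.

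The effect on Scheme 1 is conditional on literal application. Rates would then be understated in all arms, with one factor for the 5/50 mg path and another for the arms that go through period 3. The ratios of about 1.7 and 1.2 assume equal true rates, completion of period 3 by all placebo patients, and both arms at the same follow-up extreme.

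A reader might infer that the plan will make the low doses look worse than placebo. The documents do not support that. They do not assign the rate to Scheme 1, a period 2 cutoff would remove the distortion, and SAP 1.1 links follow-up length to B-cell recovery, so the direction could reverse. Nor would each arm have its own factor by design, since 5 and 50 mg share one path.

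**What to change.** - **Scheme 1:** use the sum of (min(cutoff, period 2 end of treatment) − first dose date + 1)/365.25 as denominator, and report per 100 patient-years.
- **Scheme 2:** run time from the first VAY736 dose (for the 150 mg group, the first 150 mg dose, as in SAP 2.4.1) to the point where event counting ends. If that point is end of study, call the result a rate per patient-year of follow-up and list it in SAP section 4 as a change from the protocol.
- **Both:** define study cutoff, name the grouping scheme for each table of this rate, and state the denominator for the safety-plan exposure-adjusted incidence rates in the same way.

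The cost is SAP wording and derivation code. No new data are needed, since the dates required are already used elsewhere in the SAP.
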